8.1 Screening

Molecular pre-screening

Not Applicable

Screening

Written informed consent must be obtained before any study specific medical procedures are performed. All screening/baseline assessments should occur within 21 days before Week 1 Day 1.

During the screening visit, inclusion and exclusion criteria will be assessed. Screening assessments to confirm eligibility must be performed prior to randomization. The results of the real time quantitative polymerase chain reaction (RQ-PCR) must be available prior to randomization and first dose of study treatment.

For details of assessments required during screening please refer to [Table 8-1](#).

Laboratory baseline assessments (including hematology, chemistry and serum pregnancy test), physical examination including extramedullary involvement, performance status, ECG, height, weight and vital signs, evaluation of all relevant medical history including cardiovascular risk factors, CML disease history, including prior TKI therapy and antineoplastic medication and prior and concomitant medication must be performed prior to the first dose of study treatment. Patients with potassium, and/or magnesium and/or total calcium levels that are < LLN at screening, must have their potassium, and/or magnesium, and/or calcium replenished through supplementation and the levels must be within normal limits prior to the first dose of study drug.

A patient who has a laboratory test (peripheral blood test) results that do not satisfy the entrance criteria may have the tests repeated. These tests may be repeated as soon as the investigator believes the re-test results are likely to be within the acceptable range to satisfy the entrance criteria, but should be completed within approximately 2 weeks of the original screening visit date. In this case, the subject will not be required to sign another Informed Consent Form (ICF), and the original patient ID number assigned by the investigator will be used. In the event that the laboratory tests cannot be performed within the screening visit window, or the re-tests do not meet the entrance criteria, or other eligibility criteria have changed and are not met anymore, the patient is considered a screen failure, and must be discontinued from the study.

A new ICF will need to be signed if the investigator chooses to re-screen the patient after a patient has screen failed, however, a new patient ID number will be assigned. All required screening activities must be performed when the patient is re-screened for participation in the study. An individual patient may be re-screened up to three times for the study. Once the number of patients screened and enrolled is likely to ensure target enrollment, the Sponsor may close the study to further screening. In this case, the patients who screen failed will not be permitted to re-screen.

8.1.1 Eligibility screening

Following registration in the IRT for screening, participant eligibility will be checked once all screening procedures are completed. The eligibility check will be embedded in the IRT system.

Please refer and comply with detailed guidelines in the IRT manual. The investigator site will then be allowed to assign treatment to the participant. For treatment assignment, please see [Section 6.3.2](#)

8.1.2 Information to be collected on screening failures

Participants who sign an informed consent form and subsequently found to be ineligible will be considered a screen failure. The reason for screen failure should be entered on the applicable Case Report Form. The demographic information, informed consent, and Inclusion/Exclusion pages must also be completed for screen failure participants. No other data will be entered into the clinical database for participants who are screen failures, unless the participant experienced a serious adverse event during the screening phase (see SAE section for reporting details).

Participants who sign an informed consent and are considered eligible but fail to be started on treatment for any reason will be considered an early terminator. The reason for early termination should be captured on the appropriate disposition Case Report Form.

8.1.3 Treatment Period

All patients will be given the opportunity to receive study treatment until the end of study treatment period as defined in [Section 6.1](#).

During the treatment phase, the patients will receive either asciminib treatment 40 mg BID, 80 mg QD or 200 mg (if T315I Mutation).

The dose can be modified, if required from the perspective of tolerance, following the guidance in [Section 6.5](#). Treatment will be administered until patient experiences treatment failure, unacceptable toxicity, disease progression, death, lost to follow-up and/or treatment is discontinued at the discretion of the investigator or withdrawal of consent.

The patients are advised to adhere to the food restrictions during the treatment (fasting status regarding study treatment administration, avoidance of prohibited concomitant medication).

8.1.4 Visit Windows

Study visits from Week 1 Day 1 to Week 2 Day 1 should be completed on the designated date [with an allowed “visit window” of +/- 2 day for Week 1 Day 1 and Week 2 Day 1]. All visits up until Week 4 day 1 need to be performed live by the treating physician on the site.

Study visits from Week 4 to Week 72 (EOT) should be completed every 4 weeks on the designated date [with an allowed “visit window” of +/- 7 days]. After Week 4 day 1, remote visits can be performed using tele-medicine approach with the exception of visits on Weeks 12, 24, 36, 48 and 72.

A delayed visit will have no impact on the next planned visit. The next visit should be completed as scheduled in order to avoid accumulation of additional weeks.

8.2 Participant demographics/other baseline characteristics

Patient demographics and baseline characteristics collected will include the following: date of birth, gender (and child bearing potential for female), race and ethnicity, height, weight, all relevant medical history including cardiovascular disease history, CML disease history,

including mutation status, and prior and concomitant medication including prior TKI therapy and antineoplastic medication.

Physical examination including extramedullary involvement, performance status, vital signs, ECGs, and laboratory assessments will be performed at screening.

Significant findings that were present prior to the signing of informed consent must be included in the Relevant Medical History/Current Medical Conditions page on the subject's eCRF. Significant new findings that begin or worsen after informed consent must be recorded on the AE page of the patient's eCRF.

The central reading of the screening ECGs as well as the results of the RQ-PCR must be available prior to the first dose of study treatment to evaluate eligibility and to stratify the patient.

8.3 Safety and tolerability

Safety assessments are specified below with the assessment schedule detailing when each assessment is to be performed.

Significant findings that were present prior to the signing of informed consent must be included in the Relevant Medical History/Current Medical Conditions page on the patient's eCRF. Significant new findings that begin or worsen after informed consent must be recorded on the AE page of the patient's eCRF.

For details on AE collection and reporting, refer to AE section.

Table 8-4 Assessments

| Assessment | Specification |
|----------------------|---|
| Physical examination | 
A complete physical examination will include the examination of general appearance, skin, neck (including thyroid), eyes, ears, nose, throat, lungs, heart, abdomen, back, lymph nodes, extremities, vascular and neurological. Information about the physical examination must be present in the source documentation at the study center and will be collected on the following visits as specified in Table 8-1 :
 
Screening Week 1 Day 1, Week 4
 
With the exception of Weeks 12, 24, 36, 48 and 72, Physical examination can be omitted for the remainder of the protocol. Significant findings that were present prior to the signing of informed consent must be included in the Medical History page on the patient's eCRF. Significant new findings that begin or worsen after informed consent must be recorded on the Adverse Event page of the patient's eCRF. Presence of extramedullary leukemic involvement will be checked with each physical examination as outlined above. Findings on physical examination consistent with extra-medullary leukemic involvement will be recorded (e.g. liver and spleen size, any other organ involvement).
 |
| Vital signs | 
Vital signs include blood pressure (supine position preferred when ECG is collected), pulse measurement, and body temperature and must be performed at the following visits as specified in Table 8-1:
 
 • Screening |

| Assessment | Specification |
|-------------------|--|
| | 
 • Week 1 Day 1 • Week 2 Day 1 • Week 4 
With the exception of Weeks 12, 24, 36, 48 and 72, Vital Signs can be omitted if for the remainder of the protocol
 |
| Height and weight | 
Height in centimeters (cm) will be measured at screening only. Body weight (to the nearest 0.2 pounds [lb] in indoor clothing, but without shoes) will be measured at screening and at subsequent time points as specified in Table 8-1:
 
 • Screening • Week 1 Day 1 
With the exception of Weeks 12, 24, 36, 48 and 72, Height and Weight can be omitted for the remainder of the protocol
 |

Performance status:

ECOG Performance status scale ([Table 8-5](#)) will be used as described in the [Table 8-1](#):

- Screening
- Week 1 Day 1
- Every 4 weeks from Week 4 to Week 72 (End of treatment) or early discontinuation in case of premature discontinuation.
- More frequent examinations may be performed at the investigator’s discretion, if medically indicated.

ECOG Performance status scale will be used as described in [Table 8-5](#).

Table 8-5 Table ECOG Performance Status Scale

| Description | Grade |
|---|-------|
| Fully active, able to carry on all pre-disease activities without restriction. | 0 |
| Restricted in physically strenuous activity but ambulatory and able to carry out work of a light or sedentary nature e.g. light housework, office work. | 1 |
| Ambulatory and capable of all self-care but unable to carry out any work activities. Up and about more than 50% of waking hours. | 2 |
| Capable of only limited self-care, confined to bed or chair more than 50% of waking hours. | 3 |
| Completely disabled. Cannot carry on any self-care. Totally confined to bed or chair. | 4 |
| Dead. | 5 |

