|--------------------------------------|----------|--------------------|---|-------------------------------------|--------------|--------|--------|---------|---------|---------|---------|---------|---------|---------|---------|---------|---------|---------|--|
| | | | | Week 1 Day 1 | Week 2 Day 1 | Week 4 | Week 8 | Week 12 | Week 16 | Week 20 | Week 24 | Week 28 | Week 32 | Week 36 | Week 40 | Week 44 | Week 48 | Week 52 | |
| Prior/concomitant medications | D | 6.2 | X | Continuous | | | | | | | | | | | | | | | |
| Physical examination | S | 8.3 | X | X | | X | X | X | X | X | X | X | X | X | X | X | X | X | |
| Extramedullary Involvement | D | 8.3 | X | X | | X | X | X | X | X | X | X | X | X | X | X | X | X | |
| ECOG Performance status | D | 8.3 | X | X | | X | X | X | X | X | X | X | X | X | X | X | X | X | |
| Height | D | 8.3 | X | | | | | | | | | | | | | | | | |
| Weight | D | 8.3 | X | X | | | | X | | | X | | | X | | | X | | |
| Vital signs | D | 8.3 | X | X | X | X | X | X | X | X | X | X | X | X | X | X | X | | |
| Laboratory assessments | | | | | | | | | | | | | | | | | | | |
| Hematology | D | 8.3.1 | X | X | X | X | X | X | X | X | X | X | X | X | X | X | X | X | |
| Chemistry | D | 8.3.1 | X | X | X | X | X | X | X | X | X | X | X | X | X | X | X | | |
| Chemistry-Hemoglobin A1c | D | 8.3.1 | X | Week 12 and as clinically indicated | | | | | | | | | | | | | | | |
| Serum Pregnancy test (if applicable) | D | | X | | | X | X | X | X | X | X | X | X | X | X | X | X | | |
| Hepatitis markers | D | | X | | | | | | | | | | | | | | | | |

| Visit name | Category | Protocol Section 8 | Screening Phase | Treatment Phase | | | | | | | | | | | | | | |
|--|----------|--------------------|-----------------|-------------------------|--------------|--------|----------------|---------|---------|---------|---------|---------|---------|---------|---------|---------|---------|---------|
| | | | | Week 1 Day 1 | Week 2 Day 1 | Week 4 | Week 8 | Week 12 | Week 16 | Week 20 | Week 24 | Week 28 | Week 32 | Week 36 | Week 40 | Week 44 | Week 48 | Week 52 |
| Liver assessments | D | | | as clinically indicated | | | | | | | | | | | | | | |
| Efficacy assessments | | | | | | | | | | | | | | | | | | |
| Blood collection for BCR-ABL1 quantification by RQ-PCR | D | 8.4.1 | X | | | X | | X | | | | X | | | X | | | X |
| | | | | | | | | | | | | | | | | | | |
| Hematologic Response Assessment | D | 8.4.1 | | | | | | X | | | X | | | X | | | | X |

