| Physical examination | S | 8.3 | X | X | X | X | X | |
| Extramedullary Involvement | D | 8.3 | X | X | X | X | X | |
| ECOG Performance | D | 8.3 | X | X | X | X | X | |
| Weight | D | 8.3 | | X | | | X | |
| Vital signs | D | 8.3 | X | X | X | X | X | |
| Laboratory assessments | | | | | | | | |
| Hematology | D | 8.4.1 | X | X | X | X | X | |
| Chemistry | D | 8.4.1 | X | X | X | X | X | |
| Chemistry-Hemoglobin A1c | D | 8.4.1 | as clinically indicated | | | | | |
| Serum Pregnancy test (if applicable) | D | 8.3 | X | X | X | X | X | |
| Liver assessments | D | | as clinically indicated | | | | | |
| Efficacy assessments | | | | | | | | |
| Blood collection for BCR-ABL1 quantification by RQ-PCR | D | 8.4.1 | | X ^β | | | X | |

| Visit Name | Category | Protocol Section 8 | Treatment Phase | | | | EOT /Early Discontinuation | 30 days Safety follow-up |
|---|----------|------------------------|-----------------|---------|---------|---------|----------------------------|--------------------------|
| | | | Week 56 | Week 60 | Week 64 | Week 68 | | |
| | | | | | | | | |
| Hematologic Response Assessment | D | 8.4.2 | | | | | X | |
| Cardiac Assessments | | | | | | | | |
| ECG | D | 8.3.2 | | X | | | X | |
| Cardiovascular risk factor assessments (including Family History) | D | 8.3.2 | | | | | X | |
| Echocardiogram | D | 8.3.2 | | | | | X* | |
| Adverse events / SAE | D | 10.1.1 | Continuous | | | | | |
| | | | | | | | | |

| Visit Name | Category | Protocol Section 8 | Treatment Phase | | | | EOT /Early Discontinuation | 30 days Safety follow-up |
|---|----------|--------------------|-----------------|---------|---------|---------|----------------------------|--------------------------|
| | | | Week 56 | Week 60 | Week 64 | Week 68 | | |
| | | | | | | | | |
| Asciminib Drug administration | D | | Continuous | | | | | |
| Antineoplastic therapies since discontinuation of study treatment | D | | | | | | X | |
| Progression status | D | | | | | X | | |
| | | | | | | | | |

X = assessment to be recorded in the clinical database or received electronically from a vendor

S = assessment to be recorded in the source documentation only

[figure not shown]
α = only applicable to Cohort C

* = If clinically indicated

** = Upon confirmed loss of MMR and/or End of Treatment

β = only applicable if the visit is in-person

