8.3.2 Cardiac Assessments

8.3.2.1 Electrocardiogram (ECG)

After the subject has rested approximately 10 minutes in a semi-supine position, standard 12-lead ECGs must be obtained in triplicate with a recommended minimal interval of 5 minutes between each ECG at the time points specified in Table 8-1, and Table 8-5. In this case recording of ECGs should be planned according to the true time of blood sample [REDACTED] rather than to the scheduled time point.

A standard 12 lead ECG will be performed:

- For Cohort A, B and C at screening and/or baseline, Week 1 day 1, Week 2 Day1, Week 4 Day 1, Week 12 Day 1, Week 24 Day 1, Week 36 Day 1, Week 48 Day 1, Week 60 Day 1, Week 72 Day 1 (end of study).
- Cohort C will require additional Week 8 Day 1 ECG in addition to the schedules mentioned above.

Table 8-2 ECG collection plan

| Week (or Cycle) | Time | ECG Type | Number of ECGs (per Visit) |
|---|---|----------|----------------------------|
| Screening/Baseline Day -21 to -1 / (all patients) | 3 serial ECGs at the screening visit | 12 Lead | 3 |
| Week 1 Day 1 | 3 serial ECGs at 2 h post dose | 12 Lead | 3 |
| Week 2 Day 1 | 3 serial ECGs pre-dose and at 2, 3, 4 h post dose | 12 Lead | 12 |

| Week (or Cycle) | Time | ECG Type | Number of ECGs (per Visit) |
|---|--------------------------------|----------|----------------------------|
| Week 4 Day 1 | 3 serial ECGs pre-dose | 12 Lead | 3 |
| Week 8 Day 1* | 3 serial ECGs pre-dose | 12 Lead | 3 |
| Week 12 Day 1 | 3 serial ECGs pre-dose | 12 Lead | 3 |
| Week 24 Day 1 | 3 serial ECGs pre-dose | 12 Lead | 3 |
| Week 36 Day 1 | 3 serial ECGs pre-dose | 12 Lead | 3 |
| Week 48 Day 1 | 3 serial ECGs pre-dose | 12 Lead | 3 |
| Week 60 Day 1 ⁺ | 3 serial ECGs pre-dose | 12 Lead | 3 |
| Week 72 Day (end of study) 1 | 3 serial ECGs 30 min post-dose | 12 Lead | 3 |
| Unscheduled or Unplanned sample | 3 serial ECGs | 12 Lead | 3 |
| 30 min +/- 5min allowed * Week 8 day 1 assessment is only applicable to Cohort C and in-person visit + only applicable to in-person visit | | | |

All ECGs performed will be independently reviewed. Instructions for the collection and transmission of these ECGs to the independent central reader will be provided in the [CABL001AUS04 ECG Manual].

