12.4 Primary objective / analysis of the primary endpoint(s)

Primary Objective(s)

To evaluate safety profile of monotherapy asciminib in CML-CP in 3L and beyond for Cohorts A, and B

Primary objective is to assess the safety profile of ABL001 (40 mg and 80 mg). For all primary safety analyses, the Safety Set will be used, unless stated otherwise.

The variables for the primary analysis are incidence and severity of AEs and SAEs, changes in laboratory values and vital signs, incidence of notable ECG abnormalities

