### **2.6.5.2 Vital signs**

Data on vital signs will be tabulated and summarized descriptively as follows:

- Number and percentage of patients who shift from non-notable at baseline to notable post- baseline. Also, bar chart with 95% CI will be presented for the notable changes.

The number and percentage of patients with notable vital sign values (high/low) in systolic blood pressure, diastolic blood pressure, pulse rate, weight and temperature will be presented by Cohort.

A listing of notable vital sign values will be produced. In the listing, the assessments collected outside of on-treatment period will be flagged.

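### Table 8-4 lets vital signs be skipped after Week 4 in a sentence whose condition is missing, so blood pressure can go 12 weeks unmeasured despite a mandatory dose hold at 160/100 mm Hg

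*Protocol*

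**What the plan says.** Protocol Table 8-1 marks vital signs at Screening and at every visit through Week 24, Weeks 8, 16 and 20 included: "Vital signs | D | 8.3 | X | X | X | X | X | X | X | X | X" (the cells run from Screening onward). The row has no footnote mark. The text of section 8 asks that participants be seen for everything in that schedule.

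Table 8-4 (section 8.3) names Screening, Week 1 Day 1, Week 2 Day 1 and Week 4 as visits where vital signs must be taken, and refers to Table 8-1 for them. It then adds: "With the exception of Weeks 12, 24, 36, 48 and 72, Vital Signs can be omitted if for the remainder of the protocol".

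Section 8.1.4 says that after Week 4 "remote visits can be performed using tele-medicine approach with the exception of visits on Weeks 12, 24, 36, 48 and 72". The five weeks are the same.

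Elsewhere the protocol marks in-person limits explicitly. The Week 60 PCR in Table 8-1 is footnoted "only applicable if the visit is in-person", and a note to Table 8-2 reads "Week 8 day 1 assessment is only applicable to Cohort C and in-person visit".

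Protocol 12.4 and SAP 2.5 list among the primary-analysis variables "changes in laboratory values and vital signs, incidence of notable ECG abnormalities". SAP 2.6.5.2 counts "patients who shift from non-notable at baseline to notable" values after baseline. In Table 6-2, 160 mm Hg systolic or 100 mm Hg diastolic requires a hold followed by a dose reduction, and section 6.5.2 allows no deviation from mandatory holds.

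**The concern.** A site cannot tell from the text which visits need vital signs. Table 8-1 asks for Weeks 8, 16 and 20, and Table 8-4 releases them. The release is either unconditional, with *if* a stray word, or conditional on something that is not printed. The text does not settle this: the parallel sentences for physical examination and for height and weight contain no *if* and are unconditional.

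The main stake is participant safety. The blood-pressure rule in Table 6-2 works only when pressure is measured, and so does its advice to start or adjust antihypertensives at 140-159 systolic or 90-99 diastolic. Section 1.1.2.2 lists hypertension among the adverse events above 10% in the 35 patients on 40 mg BID, which is Cohort A's regimen.

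The lesser stake is the vital-signs summary. The chance that a patient is ever recorded as notable rises with the number of readings, and the SAP does not report that number.

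**Working it through.** **Inputs.** Visit weeks and marks come from Table 8-1, permitted omissions from Table 8-4, and the window of 7 days either side from Week 4 onward from section 8.1.4. SAP 2.1.1 takes baseline as the last assessment on or before the start of study medication. Screening and Week 1 Day 1 are therefore not counted as post-baseline; both tables require them. The plan states no number of readings, so there is no figure of its own to reproduce.

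**1. Post-baseline readings to Week 24**
- Table 8-1: Weeks 2, 4, 8, 12, 16, 20, 24 = 7.
- Table 8-4 minimum: Weeks 2, 4, 12, 24 = 4.

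**2. Longest gap to Week 24**
- Table 8-1: intervals after Week 4 are 4, 4, 4, 4, 4, so 4 weeks.
- Table 8-4: 12 − 4 = 8 and 24 − 12 = 12, so 12 weeks.
- If the first visit is a week early and the second a week late, these become 4 + 2 = 6 and 12 + 2 = 14 weeks.

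**3. After Week 24**
- The Table 8-4 minimum to Week 72 is Weeks 2, 4, 12, 24, 36, 48, 72 = 7 readings, with a longest gap of 72 − 48 = 24 weeks.
- Table 8-1 marks Weeks 56, 60, 64 and 68 within that gap. If its four-weekly marks run unbroken, it gives 2 + 17 = 19 readings. The Week 52 cell appears blank in the extracted table, which may be an extraction fault; without it the count is 18. Nothing below depends on this.

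**4. Delay before a raised pressure is seen.** Assume a sustained, asymptomatic rise with onset uniform over Weeks 4 to 24, no unscheduled reading, and the permission either fully used or not used. The mean delay within an interval is half its length, and intervals are weighted by length.
- Table 8-1: 4 / 2 = 2.0 weeks; maximum 4.
- Table 8-4: (8 × 4 + 12 × 6) / 20 = 104 / 20 = 5.2 weeks; maximum 12.
- Share of onsets with a delay over 4 weeks: 0% against [(8 − 4) + (12 − 4)] / 20 = 12 / 20 = 60%.

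No assumed rate of hypertension enters this calculation.

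**5. Is omission limited to remote visits anywhere?** The match with section 8.1.4 points that way. However, the vital-signs row lacks the in-person footnote that the same table gives the Week 60 PCR. The weight row is already blank at Weeks 8, 16 and 20, and the vital-signs row is not. No text for vital signs states the limit.

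**The case against.** The strongest reply is that the two tables work together. The vital-signs row of Table 8-1 points to section 8.3, so Table 8-1 gives the planned visits and Table 8-4 the permitted relaxation. Section 8 says participants *should* be seen for all assessments, while Table 8-4 reserves *must* for Screening to Week 4. Physical examination follows the same pattern, with marks at Weeks 8, 16 and 20 and a matching permission to omit, so this looks like a convention. Adverse events are sought at every visit, and section 14 allows extra safety assessments case by case.

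Much of this stands. The purpose is evidently telemedicine, and sites may still measure at the released visits. But the cross-reference leads to an incomplete sentence, and if that sentence is taken as the permission, it covers in-person visits too. Neither adverse-event questioning nor section 14 schedules a reading for a patient without symptoms.

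Two stronger readings are tempting:
- **That uneven reading counts bias the primary result or the comparison of Cohorts A and B.** The documents do not support this. Both cohorts share one schedule, no hypothesis is tested, the summaries are descriptive, and the endpoint in Table 2-1 names adverse events, serious adverse events and laboratory evaluation only. The effect on the notable-value count cannot be sized from the documents, which give neither a per-visit rate nor a within-patient correlation.
- **That laboratory data can lapse at remote visits in the same way.** They are required at every scheduled visit (section 8.3.1, Table 8-6), an off-site draw is not barred, and the Laboratory Manual, not available here, may cover it.

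**Conclusion.** The defect is real but limited. As written, Table 8-4 allows blood pressure to be skipped at Weeks 8, 16 and 20 however the visit is conducted, with the reduced counts and longer gaps shown above. The counts and nominal gaps follow directly from the two tables. The delay figures also rest on the assumptions in step 4 and compare full use of the permission with none; actual practice will lie between.

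This is more than tidying, because a mandatory dose rule depends on a measurement that the text makes optional. It does not threaten the trial's statistical conclusions: for the vital-signs summary the consequence is an unreported difference in how often patients were measured.

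**What to change.** 1. **Table 8-4:** complete the sentence so that, after Week 4, vital signs may be omitted only when the visit is remote, with Weeks 12, 24, 36, 48 and 72 always measured on site.
2. **Table 8-1:** put the existing in-person footnote on the vital-signs cells for the weeks when a remote visit is allowed.
3. **Remote visits:** where feasible, record a blood pressure at the blood draw that stays due every 4 weeks. Items 1 and 2 stop in-person skipping, but a patient seen remotely at Weeks 16 and 20 would still have a 12-week gap; this item closes it.
4. **SAP 2.6.5.2:** report the number of post-baseline readings per patient, by cohort, beside the notable-value table.

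The cost is one sentence, one footnote mark and one added summary, with the protocol changes carried in an amendment. Item 3 adds a small site burden and depends on who does the draw and where, which the protocol does not say. For visits already completed, only item 4 can help.
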